12 DEVICE ACCOUNTABILITY

12.1 Access to Devices

Investigational rings (VR101 devices and sham rings) will be stored in a locked cabinet that will only be accessible by the PI and study coordinator. Only the study coordinator and designated staff members will have access to this cabinet and to the Device Accountability log, which contains the list of device numbers assigned to each subject.

J3 Bioscience, Inc.	Clinical Investigation Plan and Protocol CI03	CI03-CIP Rev. 02 Page 46 of 60
	A Clinical Investigation to Evaluate Efficacy of the J3 Bioscience Lubricating Intravaginal Ring VR101 as a Personal Lubricant Device in Women	

12.2 Physical Location of Investigational Devices

The Sponsor shall keep records to document the physical location of all investigational devices from shipment of investigational devices and shams to the investigation sites until return or disposal.

12.3 Use of Devices

Investigational devices and sham rings shall only be used in a manner specified by this CIP and the clinical protocol.

12.4 Distribution of Devices from the Sponsor to Clinical Sites

The Sponsor will deliver a specified number of VR101 and sham samples to each clinical site. Each clinical site will maintain Device Accountability Logs (see below), to which an entry must be made each time a VR101 or sham ring is given to a participant, or unused spare or used VR101 or sham ring is returned to the clinic by a participant.

12.5 Device Accountability Log

The principal investigator, study coordinator or an authorized designee shall keep a Device Accountability Log for VR101 and sham rings which shall include:

- The date of receipt and number of devices received from the Sponsor.
- The lot number or any other unique identifier of the rings received.
- The expiration date of rings received, if applicable.
- The number and unique IDs of rings administered to each participant, along with their unique participant identifier, and the date issued.
- The number of unused rings returned by each participant, along with their unique participant identifier, device identifiers and the date.

13 ADVERSE EVENTS, ADVERSE DEVICE EFFECTS AND DEVICE DEFICIENCIES AND REPORTING EVENTS AND DEFICIENCIES

All Adverse Events reported by participants or observed by a clinician during the study and whether or not Device Related, must be recorded using the Adverse Event Form. All Adverse Event Forms must be provided to the Sponsor. Certain Adverse Events must be reported to the Sponsor, IRB and/or FDA as they occur throughout the study (see below and in Sections 13.7 through 13.11).

SAEs and SADEs (as defined below) are to be reported to the Sponsor and IRB within 24 hours of the PI becoming aware of their occurrence.

J3 Bioscience, Inc.	Clinical Investigation Plan and Protocol CI03	CI03-CIP Rev. 02 Page 47 of 60
	A Clinical Investigation to Evaluate Efficacy of the J3 Bioscience Lubricating Intravaginal Ring VR101 as a Personal Lubricant Device in Women	

All ADEs (as defined below) are to be reported to the Sponsor within 5 days of their occurrence if study staff determines that they are possibly, probably or definitely related to use of an investigational device (VR101 or sham ring).

13.1 Definitions

Definitions below were constructed based on guidance from and definitions provided in ISO 14155 and 21 CFR 812.3.

Adverse Event (AE): Any untoward medical occurrence, unintended disease or injury, or untoward clinical signs (including abnormal laboratory findings) in subjects, users or other persons, whether or not related to VR101 use.

Serious Adverse Event (SAE): An AE that leads to:

- Death
- A serious deterioration in the health of the participant, that resulted in any of the following:
 - A life-threatening illness or injury
 - A permanent impairment of a body structure or a body function
 - In-patient or prolonged hospitalization
 - Medical or surgical intervention to prevent life-threatening illness or injury or permanent impairment to a body structure or a body function
- Fetal distress, fetal death or a congenital abnormality or birth defect.

Adverse Device Effect (ADE): An AE related to use of VR101.

Serious Adverse Device Effect (SADE): An ADE that results in any of the consequences characteristic of a SAE.

Unanticipated Serious Adverse Device Effects (USADE): Any SADE that was not previously identified in nature, severity, or degree of incidence in this CIP or application (including a supplementary plan or application), or any other unanticipated serious problem associated with a device that relates to the rights, safety, or welfare of subjects.

Use Error: Act or omission of an act that results in a different response to VR101 than intended or than expected by the user.

Device Deficiency: Inadequacy of a medical device (VR101) with respect to its identity, quality, durability, reliability, safety or performance.

The following table, copied from ISO 14155:2011, summarizes how adverse events will be categorized.

Adverse event categorization

Table F.1 presents categories of adverse events.

Table F.1 — Categories of adverse events

ADVERSE EVENTS	Non-device-related	Device- or procedure-related	
Non-serious	Adverse Event (AE)^a (3.2)	Adverse Device Effect (ADE) (3.1)	
Serious	Serious Adverse Event (SAE)^b (3.37)	Serious Adverse Device Effect (SADE) (3.36)	
		Anticipated	Unanticipated
		Anticipated Serious Adverse Device Effect (ASADE) (3.42, Note)	Unanticipated Serious Adverse Device Effect (USADE) (3.42)
a Includes all categories. b Includes all categories that are serious.			

13.2 Anticipated Adverse Events (AE)

Following is a list of adverse events that may occur during CI03:

- Discomfort/pain/pressure (vaginal, abdominal)
- Vaginal/cervical tissue irritation
- Itching
- Burning
- Vaginal discharge/excess vaginal secretion
- Malodor
- Non-menstrual vaginal/cervical bleeding
- Nausea
- Coital problems
- Penis discomfort (pain, itching, irritation)
- Increased urinary urge
- Increased incontinence
- Constipation
- Bowel obstruction
- Infection (e.g., Bacterial Vaginosis, Yeast Infection, Urinary Tract Infection)

13.3 Anticipated Adverse Device Effects (ADE)

Following is a list of adverse events that may be related to the use of VR101 or the sham:

- Device-related discomfort/pain

J3 Bioscience, Inc.	Clinical Investigation Plan and Protocol CI03	CI03-CIP Rev. 02 Page 49 of 60
	A Clinical Investigation to Evaluate Efficacy of the J3 Bioscience Lubricating Intravaginal Ring VR101 as a Personal Lubricant Device in Women	

- Device-related cramping
- Device-related vaginal itching/burning/irritation
- Device-related non-menstrual bleeding
- Toxic-shock syndrome
- Ring adherence to the vaginal wall
- Inability of user to remove the ring
- Bowel obstruction
- Ring breakage that causes injury
- Device-related infection
- Device-related vaginal/cervical/urethral irritation/inflammation
- Device-related malodor
- Device-related vaginal discharge (e.g., excessive lubrication / secretions)
- Device-related incontinence
- Intermittent Nausea
- Intermittent Headache
- Physical interference with other intravaginal or intrauterine devices

Some anticipated ADEs listed above are hypothetical, and some have been observed clinically. Refer to reports for CI01 and CI02 for a complete list of observed ADEs (either definitely or potentially related to VR101 use) and their frequency.

13.4 Device Deficiencies

Following is a list of device deficiencies that may be related to failure of VR101 or sham to meet its acceptance criteria:

- Outer polymeric ring is damaged - no release of contents
- Outer polymeric ring is damaged - release of contents
- Ring weld fails - no release of contents
- Ring weld fails - release of contents
- Device has rough surfaces
- Device will not stay in place
- Device is contaminated (on removal from package, extraneous matter is observed)
- Device is too rigid
- Device is too soft
- Device is too large
- Device is too small
- Device is too slippery
- Device cannot be easily inserted
- Device cannot be easily removed
- Instructions are missing and/or hard to follow
- Packaging is difficult to open
- Device is not biocompatible

J3 Bioscience, Inc.	Clinical Investigation Plan and Protocol CI03	CI03-CIP Rev. 02 Page 50 of 60
	A Clinical Investigation to Evaluate Efficacy of the J3 Bioscience Lubricating Intravaginal Ring VR101 as a Personal Lubricant Device in Women	

Per the Clinical Hazard Assessment, the residual risks associated with the above device deficiencies are adequately mitigated and/or are outweighed by the potential Clinical Benefits of VR101.

13.5 Possible Use Errors

Following are possible use errors, which do not indicate failure of VR101 or sham to meet its specifications:

- Placement of ring in the urinary tract
- Placement of ring in the anus or colon
- Oral contact with the device
- Use of damaged device
- Use of contaminated device (packaging damaged)
- Use of user-contaminated device
- Use of user-damaged device

13.6 Unanticipated Serious Adverse Events

Unanticipated Serious Adverse Events (USAEs) are adverse events occurring during the course of a clinical study that meet the following criteria:

- Serious
- Unanticipated
- Definitely, probably, or possibly related to the investigational device or sham

An unanticipated adverse event is any adverse event occurring in one or more subjects participating in a research protocol, whose nature, severity, or frequency is not consistent with either:

- The unknown or foreseeable risk of adverse events associated with the procedures involved in the research that are described in the protocol related-documents, such as the IRB-approved research protocol, and applicable investigator brochure, and the current IRB-approved informed consent document, and other relevant sources of information, such as product labeling, including instructions for use.
- The expected natural progression of any underlying disease or condition of the participant(s) experiencing the adverse event.

13.7 Adverse Event Reporting Procedures

13.7.1 Unanticipated Adverse Device Effect Reporting

The FDA's Investigational Device Exemption (IDE) regulations define an unanticipated adverse device effect (UADE) as, "any serious adverse effect on health or safety or any life-threatening problem or death caused by, or associated with, a device, if that effect, problem, or death was not previously identified in nature, severity, or degree of incidence in the investigational plan or application (including a supplementary plan or application),

J3 Bioscience, Inc.	Clinical Investigation Plan and Protocol CI03	CI03-CIP Rev. 02 Page 51 of 60
	A Clinical Investigation to Evaluate Efficacy of the J3 Bioscience Lubricating Intravaginal Ring VR101 as a Personal Lubricant Device in Women	

or any other unanticipated serious problem associated with a device that relates to the rights, safety, or welfare of subjects” (21 CFR 812.3(s)).

UADEs must be reported by the clinical investigator to the Sponsor and the reviewing IRB, as described below:

- Investigators are required to submit a report of a UADE to the Sponsor and the reviewing IRB as soon as possible, but in no event later than 8 working days after the investigator first learns of the event (§ 812.150(a)(1). The FDA requirement is for reporting within 10 days, which has been reduced by 2 days to allow more time for investigation).
- Sponsor must immediately conduct an evaluation of a UADE and must report the results of the evaluation to FDA, all reviewing IRBs, and participating investigators within 10 working days after the Sponsor first receives notice of the effect (§§ 812.46(b), 812.150(b)(1)).
- [From 21 CFR 812.46 (b)(2)]: A Sponsor who determines that an unanticipated adverse device effect presents an unreasonable risk to subjects shall terminate all investigations or parts of investigations presenting that risk as soon as possible. Termination shall occur not later than 5 working days after the Sponsor makes this determination and not later than 15 working days after the Sponsor first received notice.

13.7.2 Adverse Event Reporting

Any adverse event (as identified above), whether anticipated or not, shall be reported by the investigator to the Sponsor as soon as possible, but in no case later than 5 days from the date of its occurrence.

AE collection will begin after consent has been obtained and continue until the final visit. Every AE or symptom will be recorded in the CRF and will include:

- Nature (Brief Description)
- Date and Time of onset
- Date and Time of resolution
- Severity
- Probability of relationship to study procedures
- Probability of relationship to the investigational device
- Action Taken
- Outcome

Based on the occurrence and intensity of AEs, coupled with results of any other observations, the Investigator, at his/her discretion and following discussion with the Sponsor, may decide to withdraw a subject or prematurely end the study for reasons of

J3 Bioscience, Inc.	Clinical Investigation Plan and Protocol CI03	CI03-CIP Rev. 02 Page 52 of 60
	A Clinical Investigation to Evaluate Efficacy of the J3 Bioscience Lubricating Intravaginal Ring VR101 as a Personal Lubricant Device in Women	

clinical safety. The date of such termination will be recorded, and appropriate treatment instituted at the discretion of the Investigator or sub-Investigator.

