1.4 Summary of Study Schedule and Study Schematic

[figure not shown]

Figure 1. Study Schematic

- After a participant has read and signed the Informed Consent Document and has met all inclusion and exclusion criteria, she will be randomized into either the VR101 device or sham ring group.
- Participants will be instructed to use the randomly assigned device continuously and exchange with a new device every 7 days for the next 4 weeks.
- Study staff will complete a follow-up call with participants on the 7th, 14th, and 21st day following randomization to remind them to remove their current device and insert a new ring.
- Participants will return for a final study visit on day 28 ± 2 where the FSFI survey will be administered.
- Participants will be offered two additional VR101 devices for a 2-week open-label extension.
- A final follow-up call will occur 1 week after the end of the open-label extension.

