
*If a participant does not elect to participate in the open-label extension, the follow-up will occur on day 35±2 instead of day 49±2. **Only if the participant elects to participate in the open-label extension ***Only if a participant decides to withdraw participation before reaching Day 26
							

J3 Bioscience, Inc.	Clinical Investigation Plan and Protocol CI03	CI03-CIP Rev. 02 Page 32 of 60
	A Clinical Investigation to Evaluate Efficacy of the J3 Bioscience Lubricating Intravaginal Ring VR101 as a Personal Lubricant Device in Women	

Visit 1 – Study Start / Randomization (Day 0)

1. Assign a Subject Number to the prospective participant and complete initial screening procedures.
2. Participants will be administered the FSFI survey (see Section 5.4.6) by a trained member of the study staff. Complete this as early as possible in the Visit, e.g., as soon as consent is obtained.
3. A staff member will conduct a Concomitant Therapy assessment, during which they will assess and record if any hormonal therapies are currently being used or have been used in the past 3 months (these may or may not disqualify the participant from enrollment, refer to Inclusion / Exclusion Criteria above). During this assessment, women still able to get pregnant will be asked about their current birth control method. If the method is allowed by inclusion / exclusion criteria (see above), they will be instructed to continue their same method. If no birth control is currently used, or their preferred method is to use condoms, they will be offered non-lubricated condoms as to allow them to participate in the study.
4. As part of the demographic assessment, participants will be queried as to their menopausal status. If a prospective participant is still able to get pregnant, she will be asked to provide a urine sample for a pregnancy test.
5. If participant meets all inclusion and exclusion criteria, they will be enrolled and given a numbered package of randomized study product. All packages will be identical in appearance and will contain 6 individually packaged study devices (either VR101 or sham ring). All packages will contain a unique number, which will be recorded by study staff.

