6. Enrolled participants will be shown to a private clinic area or restroom to self-insert one of the devices from the package. Participants will be asked to insert one of these rings per the instructions for use and without clinician input. If a participant has difficulty with placement, she can ask for further instruction or choose to not place the ring and will be withdrawn from the study (this will be recorded on an Early Termination CRF and reported to the Sponsor). If the ring was successfully placed, the participant will be instructed to leave the first ring in the vagina for 7 days.

NOTE: Used rings / packaging are not intended to be collected by study staff. However, the site Study Coordinator may consult the Sponsor to determine if used devices / packaging should be collected in case of any unusual patient reports / adverse events.

7. Study staff will record the date and time that the ring was successfully placed and note any assistance needed from study staff (e.g., physical, verbal) so that it can be recorded in the Ring Use Log (Section 5.4.8).
8. Participants will be instructed to exchange with a fresh ring on day 7, day 14 and day 21.

J3 Bioscience, Inc.	Clinical Investigation Plan and Protocol CI03	CI03-CIP Rev. 02 Page 33 of 60
	A Clinical Investigation to Evaluate Efficacy of the J3 Bioscience Lubricating Intravaginal Ring VR101 as a Personal Lubricant Device in Women	

NOTE: If the ring is expelled (unless on a normal exchange day), the participant will be asked to rinse it using tap water and reinsert unless it is not appropriate to reinsert the expelled ring (e.g., lost in toilet, soiled). If participant is unable or unwilling to reinsert the expelled ring, or if the ring has been out for more than 24 hours, she will be asked to store it, if possible, in a provided re-sealable bag and bring it to her next clinic visit. If this occurs:

- If expelled After the ring had been inserted for at least 6 days: she will be asked to start her next scheduled ring a day early.
- If the ring had only been inserted for 5 days or less: she will be asked to insert a new ring, which will be removed on the next scheduled day (e.g., day 7, 14, 21 or 28).

Visit 2 – Final visit, Treatment week 4 (Day 28 ± 2)

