5.4.5 Terminal Follow-Up Procedure

One (1) week after the last ring is removed, each participant will be contacted to assess her medical condition and to complete a brief questionnaire. Each participant will also be reminded that she may contact the clinic at any time after the study if she is experiencing any discomfort that she believes may be related, directly or indirectly, with use of the ring. If the participant participated in the two-week open-label extension, study staff will query the participant to complete the ring use log (see Section 5.4.8). If a participant is terminated early and returns to the clinic for a final visit (see above), all information and rings can be collected during this visit and an additional follow-up call is not needed.

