### 3.2 Safety Endpoints

All adverse events (AE) and adverse device events (ADE) as well as any Serious AEs or ADEs will be recorded throughout the study and will be assessed for severity and relatedness to VR101 use. Each type of event is described, and examples are listed in the CI03 CIP.

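### Protocol 13.7.2 ends adverse-event collection at the final visit (Day 28), while Table 7 continues it to the follow-up call on Day 49 or Day 35

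*Protocol*

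**What the plan says.** **End of AE collection.** Protocol 13.7.2 is the one sentence that gives both a start and a stop: "AE collection will begin after consent has been obtained and continue until the final visit". Neither document formally defines *final visit*, but the usage is consistent. Protocol 1.4 says "Participants will return for a final study visit on day 28 ± 2 where the FSFI survey will be administered". The procedures heading for Visit 2 in 5.4.3 gives it the same name, and so does SAP 1.6.

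The later contact is always a phone call. Table 7 names it Final PC, on Day 49 ± 2, and marks the Adverse Events row in that column. Its footnote adds: "If a participant does not elect to participate in the open-label extension, the follow-up will occur on day 35±2 instead of day 49±2". Protocol 5.3.4 counts the open-label period and this call within participation, up to 49 days in all. On AEs and adverse device events, SAP 3.2 says they "will be recorded throughout the study", and Protocol 1.3.2 says the same.

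**Early terminators.** Protocol 5.4.5 opens with a general rule: one week after the last ring comes out, "each participant will be contacted to assess her medical condition". The same paragraph then makes an exception for a woman who terminates early and comes back to the clinic: "all information and rings can be collected during this visit and an additional follow-up call is not needed".

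**The concern.** The protocol gives two different ends for the same data. A site that works from Section 13 would close AE collection at the visit where open-label VR101 is handed out. A site that works from Table 7 would keep it open for up to three more weeks. There are two sites, and nothing tells them which text governs.

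The period in dispute matters for safety. It is when women randomized to sham first use VR101, and when VR101-arm women reach their longest exposure. Protocol 2.1 says CI03 is to continue monitoring VR101 safety and that its data will support a 510(k). The SAP text available for review states no AE window or exposure denominator that would settle the question, and its Section 6 covers efficacy analyses only.

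The 5.4.5 waiver raises a related, smaller question. After the early-termination visit, no scheduled contact looks for new events in the women it covers.

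**Working it through.** No power or alpha figure bears on this point. The check is a day count and a comparison of texts.

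**Inputs.** Blinded phase 28 days, open-label phase 14 days, follow-up 7 days (Protocol 5.3.4). Windows of ± 2 days at Visit 2 and at the Final PC (Table 7). Minimum of 80 women per arm (Protocol 1.1). Early terminators 9 of 175, all with a final FSFI lubrication score (SAP Section 12, Table 1).

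**Reproducing the plan's own figures.** 28 + 14 + 7 = 49 days, which matches 5.3.4 and the Day 49 call. Without the extension, 28 + 7 = 35 days, which matches the Table 7 footnote.

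**Gap between the two stop points.**
- With the extension: 49 − 28 = 21 days; 21/49 = 42.9%. With both windows, 21 ± 4, so 17 to 25 days. Of the nominal 21 days, 14 are on VR101 and 7 are after removal.
- Without the extension: 35 − 28 = 7 days; 7/35 = 20%. With both windows, 7 ± 4, so 3 to 11 days. All are after removal.
- If 13.7.2 ran to the Final PC, the gap would be 0 days in both cases.

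**VR101 exposure inside the gap, per woman taking the extension.**
- VR101 arm: 14/(28 + 14) = 14/42 = 33.3% of her VR101 days.
- Sham arm: 14/14 = 100% of her VR101 days.

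**Illustration across the trial.** Extension uptake is not given in the text available, so it is an assumption here: uptake *u*, equal in both arms, with full adherence and 80 women per arm. Blinded VR101 use is 80 × 4 = 320 device-weeks. Open-label use is 160 × 2 × *u* = 320*u*. The share of VR101 device-weeks after Visit 2 is 320*u*/(320 + 320*u*) = *u*/(1 + *u*):
- *u* = 0: 0%
- *u* = 0.5: 33.3%
- *u* = 1: 50%

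**Early terminators.** 9/175 = 5.1%. The waiver applies only to those who return to the clinic. All nine have a final score, so it could have applied to as many as nine. How much post-removal time the visit covers depends on when the ring came out, which the documents do not say. If it came out at the visit, 0 of the 7 post-removal days are covered by any scheduled contact.

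**The case against.** The strongest reply is that one loosely worded phrase stands against many operative provisions:
- Table 7 lists AEs at the Final PC.
- The opening of Section 13 requires every AE reported during the study to be recorded.
- Protocol 6.3.2 has staff monitoring AEs throughout CI03.
- SAP 1.2 and 1.6 describe a safety follow-up after the extension.
- SAP 10.2 shows that the post-extension call was in use.

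This stands, and it limits the finding. A reader might infer from 13.7.2 that every open-label event is lost. The documents do not support that: a site that follows Table 7 records those events.

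A reader might also infer that both rules lower the observed VR101 event rate. That is not shown. The 5.4.5 waiver applies to both blinded arms alike. Stopping at Day 28 removes exposure as well as events, so whether a rate falls depends on the denominator used and on when events occur, and the documents give neither.

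On 5.4.5, the reply is that the waiver is an express exception, limited to women who attend a visit where AEs are collected, and that Protocol 5.3.6 sends women who leave because of an AE to the follow-up in 13.10. This also largely stands. Section 13.10 follows device-related events already present and does not look for new ones, so a gap remains, but whether to close it is a design choice. It might also be inferred that the women covered by the waiver are those most likely to have stopped because of the ring. The text available does not give the nine women's reasons for stopping.

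Finally, Protocol 2.1 records that FDA and the sponsor agreed safety had already been demonstrated. That lowers the stakes but does not settle which stop point applies.

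**Conclusion.** The conflict between 13.7.2 and Table 7 is real and should be corrected. On the documents' own usage, 13.7.2 stops AE collection 21 days (43% of participation) before the last scheduled AE contact for women in the extension, and 7 days (20%) before it for the others. The consequence is conditional: events in those days could go unrecorded where 13.7.2 is followed over Table 7. This rests on reading *final visit* as Visit 2, which the protocol and SAP 1.6 support but no definition fixes. The only other use, for the early-termination visit in 5.4.5, is earlier still.

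The 5.4.5 waiver is a secondary matter of reconciliation. It affects at most the nine early terminators (5.1% of those treated), who may lack post-removal AE follow-up.

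**What to change.** 1. In Protocol 13.7.2, make the end of AE collection the Final PC in Table 7: Day 49 ± 2, or Day 35 ± 2 without the extension.
2. Reconcile the waiver in 5.4.5 with that section's opening rule and with Table 7, whose footnote does not say whether early terminators receive the call. The documents should state one rule; which one is for the sponsor and investigators to decide.
3. In the study report, state the AE window actually used, count exposure over that same window, and note that early terminators may lack post-removal AE follow-up.

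The cost is one phrase in 13.7.2, one clarifying sentence in 5.4.5, and a short statement in the report. SAP 10.1 says data collection was complete before the blind was broken, so the wording changes cannot recover events that were not collected. For this trial, the third item does most of the work.
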